2.1. Objective

To evaluate the relative efficacy of three commonly utilized regional corticosteroids for the regional treatment of uveitic macular edema: periocular triamcinolone acetonide; intravitreal triamcinolone acetonide; intravitreal dexamethasone implant. The primary efficacy measure will be percent change in central subfield thickness as measured by OCT at 8 weeks. Participants will continue in the study for 24 weeks in order to evaluate relative effects of the 3 treatment strategies on the duration of treatment effects, requirement for additional injections, and adverse effects.

2.2. Hypothesis

Primary hypotheses:

- (1) Intravitreal triamcinolone injections will have greater efficacy than periocular triamcinolone as a treatment for uveitic macular edema.
- (2) Intravitreal injections of the dexamethasone pellet will have greater efficacy than periocular triamcinolone injections as a treatment for uveitic macular edema.
- (3) Intravitreal injections of the dexamethasone pellet will be non-inferior to intravitreal triamcinolone as a treatment for uveitic macular edema.

Secondary hypothesis:

- (1) Intravitreal injections of the dexamethasone pellet will have a lower rate of IOP elevation than intravitreal triamcinolone injections over the 24 weeks of follow-up.

3. Design

[figure not shown]
3.1. Type of study

- Three-armed, parallel design randomized comparative trial
- Allocation ratio 1:1:1
- Randomization stratified by the presence or absence of concomitant systemic therapy for uveitis (e.g., oral corticosteroids and/or immunosuppressive drugs)
- Unit of randomization is patient, not eye; if both eyes meet eligibility criteria, both receive the assigned treatment
- Multicenter
- Fixed sample size, 267 (89 per treatment group)
- Anniversary close-out at the 24 week clinic visit
- Reading center graders assessing primary outcome and visual acuity examiners masked to treatment
- Open-label; treating physicians and patients unmasked to treatment (the therapies are different in appearance and have potentially different injection schedules)

3.2. Treatment Arms

- Periocular triamcinolone acetonide (Kenalog) (40 mg)
- Intravitreal triamcinolone acetonide (preservative-free preparation, Triesence at U.S. clinics; Triesence preferred at non-U.S. clinics but Kenalog allowed) (4 mg)
- Dexamethasone intravitreal implant (Ozurdex) (0.7 mg)

3.3. Trial schema

* Eye(s) meeting trial eligibility criteria receive initial injection of assigned treatment at P01 visit.

† Second injection of assigned treatment permitted at 8 week visit or later for periocular and intravitreal triamcinolone acetonide and at 12 week visit or later for intravitreal dexamethasone when following conditions are met:

- Eye does not meet the improvement definition (a 20% decrease in central subfield thickness of the macula) OR eye has a normal central subfield thickness but has cystoid spaces in the 1 mm central subfield OR ME is worse after initial improvement;
- IOP of <25 mm Hg and treatment with ≤3 IOP-lowering agents;

‡ Eyes demonstrating < 20% reduction or worsening of ME as measured by the central subfield macular thickness on OCT are considered primary treatment non-responders at these time points

§ Macular Edema Ranibizumab v. Intravitreal Anti-inflammatory Therapy (MERIT) Trial is a companion study to POINT (funded by the same grant) for treatment of macular edema persisting after intravitreal triamcinolone therapy. MERIT will begin enrollment approximately 1 year after the initiation of POINT and continue concurrently. POINT participants who meet MERIT eligibility criteria at indicated time points may enroll in MERIT while concurrently completing follow-up in POINT. MERIT will evaluate the relative effectiveness among two regionally-administered alternatives to regional corticosteroid injections, a) intravitreal ranibizumab (Lucentis®, Genentech Inc., San Francisco, CA), and b) intravitreal methotrexate (MTX), with c) the intravitreal dexamethasone (Ozurdex) for the treatment of uveitic macular edema persistent after intravitreal corticosteroids.

3.4. Primary outcome

The primary outcome is the percent change in central subfield thickness from the baseline OCT measurement at the 8-week visit. The time point of 8 weeks was chosen for assessment of the primary outcome because it encompasses the window for maximum benefit for all three treatment strategies. The results will be transformed to represent relative change. Assessment of OCT outcomes will be performed by masked readers.

3.5. Secondary outcomes

- Rate of IOP elevation of >21 mm Hg or \geq 10 mm Hg from baseline during the 24 weeks of follow-up
- Percent change in macular thickness as measured by OCT over the 24 weeks of follow-up
- Proportion of eyes with macular edema events over the 24 weeks of follow-up
 - \geq 20% reduction in macular thickness (or normalization of macular thickness even if there is <20% reduction)
 - "Resolution", defined as normalization of the macular thickness to within \pm 2 standard deviations of the normative mean for the OCT machine used
 - Worsening defined as a 20% increase in macular thickness from the lowest value after an injection
 - "Recurrence" defined as >20% increase in the central subfield measurement on OCT to an abnormal value in an eye that previously had resolution of ME
- Mean change in BCVA over the 24 weeks of follow-up.
Best-corrected visual acuity score will be measured at every study visit under standardized lighting conditions by certified study examiners masked to study treatment using logarithmic (ETDRS) visual acuity charts, according to the method described by Ferris, et al.⁷⁵
- Inflammation as graded using the semi quantitative scales used in the MUST Trial i.e., clinician grading of the presence and extent of anterior chamber cells, anterior vitreous cells, and vitreous haze based on previously published standard ordinal scales (0, trace, 1+, 2+, 3+, 4+)⁷⁶⁻⁷⁸ using the scales endorsed by the Standardization of Uveitis Nomenclature Working Group when applicable⁷⁹
- Safety outcomes including elevated IOP (>30 mm Hg thresholds); new onset posterior subcapsular (PSC) cataract or progression of pre-existing PSC (using the Age-Related Eye Disease Study [AREDS] scheme⁸⁰; vitreous hemorrhage; retinal tear/detachment; endophthalmitis; severe vision loss (\geq 15 Early Treatment Diabetic Retinopathy Study [ETDRS] letters) during the 24 weeks of follow-up.
- Cost-effectiveness of treatments for uveitic macular edema during the 24 weeks of follow-up will be assessed by enumerating costs of treatments and procedures for uveitis during the 24 week follow-up; participants' utilities will be measure with the EuroQol questionnaire.
- Visual function related quality of life as measured by the NEI Visual Function Questionnaire (25 item version).

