3.6. Eligibility criteria

Inclusion criteria:

Patient level inclusion criterion:

1. 18 years of age or older;

Eye level inclusion criteria - at least one eye must meet all of the following conditions

2. Non-infectious anterior, intermediate, posterior or panuveitis; either active or inactive uveitis is acceptable;
3. Macular edema (ME) defined as the presence of central subfield macular thickness greater than the normal range for the OCT machine being used ($>300\ \mu\text{m}$ for Zeiss Cirrus/Topcon 3DOCT or $>320\ \mu\text{m}$ for Heidelberg Spectralis), regardless of the presence of cysts, as assessed by study ophthalmologist;
4. Best corrected visual acuity (BCVA) 5/200 or better;
5. Baseline intraocular pressure $> 5\ \text{mm Hg}$ and $\leq 21\ \text{mm Hg}$ (current use of 3 or fewer intraocular pressure-lowering medications and/or prior glaucoma surgery are acceptable – *note that combination medications, i.e., Cosopt, count as 2 IOP lowering medications*);
6. Baseline fluorescein angiogram that is gradable for degree of leakage in the central subfield
7. Pupillary dilation sufficient to allow OCT testing.

Exclusion criteria:

Patient level exclusion criteria:

1. History of infectious endophthalmitis or infectious uveitis in either eye;
2. History of infectious scleritis of any type in either eye. (*Note: History of noninfectious scleritis that has been active in past 12 months is an eye-level exclusion –see #11 below.*)
3. History of keratitis (with the exception of keratitis due to dry eye) in either eye;
4. History of central serous retinopathy in either eye;
5. For women of childbearing potential: pregnancy, breastfeeding, or a positive pregnancy test; unwilling to practice an adequate birth control method (abstinence, combination barrier and spermicide, or hormonal) for duration of trial;
6. Use of oral acetazolamide or other systemic carbonic anhydrase inhibitor at baseline;
7. Oral prednisone dose $> 10\ \text{mg}$ per day (or of an alternative corticosteroid at a dose higher than that equipotent to prednisone $10\ \text{mg}$ per day) OR oral prednisone dose $\leq 10\ \text{mg}$ per day at baseline that has not been stable for at least 4 weeks (*note that if patient is off of oral prednisone at baseline (P01 visit), dose stability requirement for past 4 weeks does not apply*);

8. Systemic immunosuppressive drug therapy that has not been stable for at least 4 weeks;

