50%, so a 40% decrease or log change in retinal thickness of $\log(0.60) = -0.5108$ was selected. Intravitreal triamcinolone is expected to have a similar level of improvement; whereas periocular triamcinolone is expected to have a smaller but clinically meaningful change, i.e. a 25% reduction or log change of $\log(0.75) = -0.2877$. Based upon a standard deviation of log-retinal thickness of 0.33, a sample size of 89 independent eyes per treatment group, i.e. 89 individuals with one eye for each individual, provides 98% power to detect a 40% reduction in retinal thickness for an intravitreal corticosteroid treatment as compared to a 25% reduction for periocular triamcinolone at 8 weeks with a two-sided type I error rate of 0.01667 (i.e. 0.05/3). This number increases to 99 individuals after inflating it for a 10% loss to follow-up. By including outcomes from both eyes for participants with bilateral macular edema (assuming a between eye correlation of 0.4 and 25% bilateral disease), we can reduce our sample size to 89 individuals enrolled in each arm (267 total). That is, 10 fewer participants per arm after accounting for losses to follow-up than are required if we only include a single eye per participant.

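### The two-sided definition of resolution scores an edema-free but thin macula as unresolved, which would tend to dilute the between-arm difference in this secondary outcome

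*Combined protocol and SAP*

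**What the plan says.** Section 3.5 lists, under "Proportion of eyes with macular edema events over the 24 weeks of follow-up", an event called resolution, "defined as normalization of the macular thickness to within" ±2 "standard deviations of the normative mean for the OCT machine used". Neither the normative mean nor the SD is given.

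Two neighbouring events use related language. The response event accepts a reduction of at least 20%, "or normalization of macular thickness even if there is <20% reduction". Recurrence requires an increase of more than 20% "to an abnormal value in an eye that previously had resolution of ME".

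Section 3.6 defines macular edema at entry as "central subfield macular thickness greater than the normal range for the OCT machine being used", with thresholds of >300 µm (Cirrus/Topcon) and >320 µm (Spectralis). There is no lower bound.

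Section 6.1 plans a 40% fall for the dexamethasone implant ("so a 40% decrease or log change in retinal thickness"), a similar fall for intravitreal triamcinolone and 25% for periocular triamcinolone. The SD of change in log thickness is 0.33.

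**The concern.** The two definitions leave an unassigned group. An eye below mean − 2 SD has neither edema by section 3.6 nor resolution by section 3.5, and nothing in the plan says how to class it. Followed literally, it counts as unresolved at that visit, alongside eyes that are still swollen. It also cannot enter the recurrence risk set unless it was inside the band at another visit.

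The error need not be balanced. Arms with larger reductions send more eyes below any fixed lower limit, so the intravitreal versus periocular comparison would tend to be diluted. The two intravitreal arms are planned with similar reductions, so no particular distortion is expected between them. Section 6.2 says secondary outcomes will be read mainly through estimates and confidence intervals, so a diluted estimate matters directly.

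**Working it through.** **The plan's nearest figure.** Section 6.1 states 99.9% and 93% power for 50% v 85% and 50% v 75% with 89 eyes per arm, two-sided 0.05. Using power = Φ{[d − 1.96·√(2p̄(1−p̄)/n)] / √([p₁(1−p₁)+p₂(1−p₂)]/n)}:

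- 50% v 85%: (0.35 − 1.96×0.0702)/0.0651 = 3.26, power 99.9%.
- 50% v 75%: (0.25 − 1.96×0.0726)/0.0701 = 1.54, power 93.8%.

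Both reproduce. However, section 6.1 says these rates probably reflect a measurable OCT reduction, not complete resolution. They are not rates of the ±2 SD event, and no figure is stated for that event.

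**Direction.** Let U and L be the upper and lower limits of the band. In each arm, resolved as written = P(≤U) − P(<L). So the difference as written equals the one-sided difference minus [P(<L) in the 40% arm − P(<L) in the 25% arm]. With the same baseline and the same spread, the bracket is positive for any L, so the difference shrinks.

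**Size, under assumptions.**

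- From section 6.1: retained fraction r = 0.60 (intravitreal) or 0.75 (periocular); SD of change in log thickness 0.33.
- Assumed: U = 300 µm. This is the Cirrus/Topcon entry threshold, but the documents do not say that it equals mean + 2 SD.
- Assumed: normative SD 15-25 µm, so L = 300 − 4×SD = 240 to 200 µm; an SD of 30 (L = 180) is added as a wider check.
- Assumed: a common baseline B, and a single visit.
- Formula: P(thickness < x) = Φ(ln[x/(B·r)]/0.33).

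Example, B = 400 and L = 220:

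- Intravitreal: P(≤300) = Φ(ln[300/240]/0.33) = Φ(0.676) = 0.751; P(<220) = Φ(ln[220/240]/0.33) = Φ(−0.264) = 0.396; within band 0.355.
- Periocular: P(≤300) = Φ(0) = 0.500; P(<220) = Φ(ln[220/300]/0.33) = Φ(−0.940) = 0.174; within band 0.326.
- Difference: 25.1 points one-sided, 2.9 points as written.

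Difference in resolution, intravitreal minus periocular, in percentage points:

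| Baseline (µm) | One-sided (≤300) | L = 240 | L = 220 | L = 200 | L = 180 |
|---|---|---|---|---|---|
| 350 | 20.3 | −6.1 | −5.7 | −3.3 | 0.9 |
| 400 | 25.1 | 0.0 | 2.9 | 7.0 | 12.0 |
| 450 | 26.4 | 5.5 | 9.5 | 14.0 | 18.4 |
| 500 | 25.1 | 9.0 | 13.0 | 16.9 | 20.3 |
| 600 | 18.0 | 10.0 | 12.8 | 15.0 | 16.5 |

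At baseline 400-500 and L = 200-240, the share of eyes below L is 11-50% in the 40% arm and 3-25% in the 25% arm. With a narrower SD of 0.20, B = 400 and L = 220, the difference goes from 37 to 10 points, so dilution does not depend on the wide SD.

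**Response event.** A fall of less than 20% from above 300 µm leaves an eye above 300×0.80 = 240 µm. On these assumed limits the lower bound therefore never bites on the normalization route, and eyes that drop below the band have already fallen by 20%.

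**The case against.** The strongest reply is that the documents give no normative values, no baseline distribution and no count of thin eyes, so the numbers rest on assumptions. That is correct. The model also has no anatomical floor and applies the same proportional fall whatever the baseline, and section 6.1 itself calls 0.33 conservative. The shares of very thin eyes above are therefore probably too high.

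A second reply is that an abnormally thin macula is not normal, so a two-sided band is a fair meaning of normalization. As a statement about normality this stands. But the event is called resolution of edema, and the entry definition does not treat thinness as edema. Thinning is worth reporting, but not in the same category as persistent swelling.

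Two stronger readings are tempting, and neither is supported:

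- A reader might infer that the rule penalises the more effective arm. Over baselines of 400-500 µm and lower limits of 200-240 µm the difference never turns negative. It reverses only at an assumed baseline near 350 µm.
- A reader might infer that a thin eye can never be at risk of recurrence. Events are counted over 24 weeks and section 3.8 schedules five post-baseline OCTs, so an eye inside the band at any visit may count as previously resolved. The plan does not say whether resolution is scored per visit or as ever reached. If it is ever reached, the loss is smaller than in the single-visit calculation.

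It is also true that the response event and the continuous thickness outcomes still capture the benefit in thin eyes.

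**Conclusion.** The mismatch is on the page: resolution has a lower limit that the entry definition of edema lacks, and followed literally the rule misclassifies edema-free thin eyes. With the plan's own 40% v 25% reductions, and a common baseline and spread, the likely effect is dilution of the intravitreal versus periocular difference. Under the stated assumptions (upper limit 300 µm, lower limit 200-240 µm, baseline 400-500 µm, log-SD 0.33, single visit), about 25 points becomes 0 to 17 points. The true loss is probably smaller, and the documents cannot fix its size.

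The effect is confined to resolution and, through it, recurrence. Section 3.4 says: "The primary outcome is the percent change in central subfield thickness from the baseline OCT measurement at the 8-week visit". That measure does not use the band, so the primary outcome, its alpha and the sample size are unaffected.

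**What to change.** In section 3.5, define resolution as thickness at or below the upper limit of normal for the machine used. State that limit and reconcile it with the 300/320 µm entry thresholds. Give normalization in the response event, and resolution and abnormal value in the recurrence event, the same one-sided meaning. Say whether resolution is scored at each visit or as ever reached. Report eyes below the lower limit separately, by arm, as thinning.

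The cost is one phrase and one extra table row, using OCT data already collected. The change should be made before outcome data are seen by arm, so that the classing of thin eyes is not a data-driven choice.

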Traditional approaches to the treatment of uveitic ME have included the use of regional corticosteroid therapy, delivered periocularly, including posterior sub-Tenon's (PST) and orbital floor injections, or via the intravitreal route.^{7, 10, 29-41} With respect to periocular delivery, available nonrandomized, but comparative, data suggest similar success rate with both approaches.⁴²⁻⁴⁴ The most commonly used drug is triamcinolone acetonide (TA) even though both methylprednisolone and TA have been used for periocular injections. The estimated pharmacologic effect of a regional corticosteroid injection, whether given by the periocular or intravitreal route, appears to be approximately 3 months, although the duration of benefit in some patients with uveitis may be longer.

In a retrospective study of 159 eyes that underwent PST for ME from a variety of etiologies and were followed for a mean of 12 months, a single injection posed relatively little risk of IOP

complications and cataract progression whereas with repeated administration, these side effects increased.⁴⁵ A study from the Johns Hopkins Medical Institution of 126 patients (156 eyes) with uveitic ME who received a single periocular injection of corticosteroid reported clinical resolution of ME among 53% and 57% of eyes at 1 month and 3 months respectively.⁴⁶ Of the 83 eyes that had resolution of ME at 1 month, 50 (60%) had no recurrence of the ME at 3 months after the first periocular corticosteroid injection. Among those eyes that had recurrence of ME, the median time for recurrence was 20 weeks. Forty eyes were treated with more than one periocular injection due to persistence of ME one month following the first injection. Of the 21 eyes treated with a second periocular injection, 81% and 43% had no ME at one and 3 months, respectively, after the second injection. Overall, a 3-line improvement in visual acuity was observed in 52% at one month and in 57% at 3-months. Side effects attributed to periocular corticosteroid injections included IOP rise to >30 mm of Hg in 19% (rate = 0.14/eye-year [EY]), newly diagnosed cataract in 10% (rate = 0.13/EY), and ptosis in 14% (rate = 0.09/EY).

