4.3.1. Administration of periocular triamcinolone acetonide

The injection may be given either by posterior sub-Tenon's approach or by the orbital floor approach, as both appear to have similar efficacy; the approach to the periocular injection will be recorded for analysis if needed.

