4.4. Possible side effects and complications of treatments

4.4.1. *Periocular triamcinolone acetonide*

Possible side effects and complications associated with periocular triamcinolone acetonide injections are similar to those associated with intravitreal injections of triamcinolone acetonide, but rates are lower because the drug is not injected directly into the eye.

- Commonly reported events
 - Elevated intraocular pressure
 - Cataract development
- Less frequently reported events
 - Ocular discomfort
 - Transient visual blurring
 - Subconjunctival hemorrhage
 - Ptosis with posterior sub-Tenon's injections (risk increases with multiple injections)
- Rare and serious events
 - Glaucoma or severe IOP elevation requiring surgical therapy
 - Breach of sclera
 - Endophthalmitis (occurs with inadvertent breach of sclera and injection of drug into the eye (less than 1 in 1000 cases))
 - Subretinal deposition of drug
 - Retinal tear with or without retinal detachment
 - Vitreous hemorrhage

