5.1. Adverse events

Adverse events (AEs) and complications of study treatment will be recorded on study data forms and submitted to the CC. The CC Safety Officer and the DSMC Safety Officer will review all adverse events and make recommendations to the DSMC as to any actions that may be needed.

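### Ptosis, an expected complication of periocular injection in the protocol's own account, is not a named safety outcome, so its ascertainment rests on general adverse event reporting in an open-label trial

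*Combined protocol and SAP*

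**What the plan says.** Section 2.1 makes the relative adverse effects of the three strategies an objective over 24 weeks. Section 3.5 names the safety outcomes: "Safety outcomes including elevated IOP (>30 mm Hg thresholds); new onset posterior subcapsular (PSC) cataract or progression of pre-existing PSC", followed by "vitreous hemorrhage; retinal tear/detachment; endophthalmitis; severe vision loss". Ptosis is not among them.

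Two other sections treat ptosis as a known effect of the periocular route:

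- Section 1.6 cites a study of 156 eyes with uveitic macular edema given periocular corticosteroid. It reports three side effects: IOP above 30 mm Hg in 19% (0.14 per eye-year), new cataract in 10% (0.13 per eye-year) and "ptosis in 14% (rate = 0.09/EY").
- Section 4.4.1 places it under the less frequent periocular events: "Ptosis with posterior sub-Tenon's injections (risk increases with multiple injections"). The lists for the two intravitreal drugs (4.4.2 and 4.4.3) do not contain it.

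Section 4.3.1 allows the periocular injection "either by posterior sub-Tenon's approach or by the orbital floor approach" and records which was used. The expected split is not given. Second periocular injections are allowed from week 8 (3.3 and 4.2.2).

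On general capture, section 5.1 states: "Adverse events (AEs) and complications of study treatment will be recorded on study data forms". Section 3.8 schedules adverse event monitoring and an ophthalmic exam at all six visits. Section 6.2 plans count models for recurring events such as the number of adverse events. Section 7.2.4 has adverse events tabulated by assigned treatment for the DSMC. Under section 3.1, treating physicians and patients are unmasked; OCT graders and visual acuity examiners are masked.

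**The concern.** Section 1.6 weighs better expected efficacy of intravitreal triamcinolone against more side effects than the periocular route. A fair reading of that trade-off needs each route's known harms ascertained in the same way in every arm. Of the three periocular side effects that section 1.6 quantifies, two became named outcomes and ptosis did not.

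General adverse event reporting will pick up some ptosis, but the plan gives it no definition, no baseline status and no check of every study eye. Unmasked staff who expect ptosis in one arm may look for it more there, or may treat it as too familiar to record. The direction of the error is not predictable. A model of total adverse event counts would not isolate it, and DSMC tables are not a planned final comparison. At stake is whether the trial can give a usable ptosis estimate by arm.

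**Working it through.** **1. The plan's own safety power.** Section 6.1 gives 99% power for IOP elevation of 12% v 40%, with 89 independent eyes per group and two-sided 0.05. The normal approximation with pooled variance under the null gives 0.992. The figure reproduces.

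**2. What the 14% measures.** If the percentage and the rate share one denominator, follow-up per eye is 0.14 / 0.09 = 1.56 eye-years, well beyond 24 weeks. The same division gives 0.19 / 0.14 = 1.36 for IOP and 0.10 / 0.13 = 0.77 for cataract. These differ, so a common denominator is itself an assumption.

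**3. Conversion to the trial's horizon.** With a constant rate, risk = 1 − exp(−rate × 24/52).

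| Side effect (1.6) | Rate per eye-year | 24-week risk |
|---|---|---|
| IOP >30 mm Hg | 0.14 | 6.3% |
| New cataract | 0.13 | 5.8% |
| Ptosis | 0.09 | 4.1% (unrounded 4.07%) |

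Ptosis is thus of the same order as two harms that section 3.5 names.

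**4. Expected events.** At 4.07%: 89 × 0.0407 = 3.6 eyes, or 4.5 if 25% of patients contribute two eyes (89 × 1.25 = 111 eyes). At 14%: 89 × 0.14 = 12.5 eyes.

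**5. Power if ptosis were compared.** Exact power of a two-sided Fisher test at 0.05, 89 v 89 independent eyes. The documents give no ptosis risk for the intravitreal arms, so 0%, 1% and 2% are assumptions.

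| Periocular risk | v 0% | v 1% | v 2% |
|---|---|---|---|
| 4.07% | 15% | 7% | 4% |
| 10% (intermediate, assumed) | 89% | 69% | 51% |
| 14% | 99% | 92% | 83% |

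As a check on the first cell: 5 v 0 events gives p = 0.059 and 6 v 0 gives p = 0.029, so at least 6 events are needed. P(X ≥ 6) for a binomial with n = 89 and risk 0.0407 is 0.155. Rounding the risk up to 4.1% gives 0.159.

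**6. Precision of an estimate.** The exact (Clopper-Pearson) 95% interval takes the 2.5% quantile of Beta(x, n − x + 1) and the 97.5% quantile of Beta(x + 1, n − x). For 4 of 89 (4.5%) it is 1.2% to 11.1%. For 12 of 89 (13.5%) it is 7.2% to 22.4%.

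**The case against.** The case against has real weight.

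- **The list is open and capture exists.** Section 3.5 introduces its list as examples. Adverse events and treatment complications are recorded, monitoring is scheduled at every visit, and DSMC tables are by arm. This stands, and it rules out saying that ptosis would go unrecorded. The data forms are not in the documents, so a ptosis field may already exist. What is missing from the plan is a definition, a check of every study eye and a commitment to report this event.
- **The omission is not one-sided.** A reader might infer that the plan makes the periocular arm look safer than it is. The documents do not support that. Implant migration and globe perforation, listed for the intravitreal drugs, are also unnamed. IOP elevation, cataract, endophthalmitis, retinal tear or detachment and vitreous hemorrhage are all listed for the periocular arm too. The two unnamed intravitreal harms do differ from ptosis: migration is tied to a non-intact capsule, and a torn or ruptured capsule is an exclusion; perforation is listed as rare.
- **Ptosis may be uncommon here.** A reader might take 14% as the expected risk and conclude that 89 eyes per arm compare ptosis with 83% to 99% power. That ignores the rate printed beside it. A reader might also infer that ptosis is commoner than cataract. That holds for the percentages but reverses for the rates (0.09 v 0.13), and section 4.4.1 classes cataract as common and ptosis as less frequent. The sub-Tenon link also lowers the expected count if many injections use the orbital floor.
- **The same unmasked examiners would score it.** True. A uniform item lessens uneven recording but does not remove open-label bias.

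**Conclusion.** The gap is real but modest. Ptosis is a complication that the protocol itself expects from one route and does not list for the other two drugs. Its ascertainment depends on general reporting by unmasked staff and may be uneven between arms. The documents show neither that the periocular arm would be favoured nor in which direction any error would run.

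The expected yield runs from about 4% over 24 weeks (about 4 of 89 eyes) to 14% (about 12 eyes). The lower figure assumes a constant rate; early clustering would raise it. The upper figure treats a percentage that appears to cover longer follow-up as a 24-week risk. Both come from one cited study in which 40 eyes had more than one injection. Extensive orbital floor use could take the yield below 4%.

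At the low end a pairwise test has almost no power, so the case for naming ptosis does not rest on testing. Section 6.2 already puts the emphasis for secondary outcomes on estimates and confidence intervals, and such an estimate is only as good as the uniformity of recording.

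**What to change.** Add new ptosis since baseline to the safety outcomes in section 3.5, with a written definition set by the clinical investigators. Score it yes/no for every study eye in all three arms, at baseline and at each ophthalmic exam in section 3.8. In section 6.2, commit to reporting it by assigned arm as a proportion with a confidence interval that allows for two eyes per patient, and to describing it by periocular approach (sub-Tenon or orbital floor). Do not present it as a powered comparison.

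The cost is one item on an existing exam form, one definition and one table row. No visit, treatment or sample size changes. The downside is slightly more recording by examiners who remain unmasked, which the report should state as a limitation. If the forms already carry a ptosis field, only the definition and the reporting commitment are needed.
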